## 9.3. Analysis Sets

For purposes of analysis, the following analysis sets are defined:

Participant Analysis Set	Description
Enrolled	"Enrolled" means a participant's agreement to participate in a clinical study following completion of the informed consent process.
Evaluable	All participants assigned to IP and who take at least 1 dose of IP.
Safety	All participants assigned to IP and who take at least 1 dose of IP.

Participant Analysis Set	Description
PK Concentration Set	The PK concentration population is defined as all participants who received at least 1 dose of PF-06882961 and in whom at least 1 plasma concentration value is reported.
PK Parameter Set	The PK parameter analysis population is defined as all participants who received at least 1 dose of PF-06882961 and have at least 1 of the PK parameters of interest calculated.

## 9.4. Statistical Analyses

The SAP will be developed and finalized before any analyses are performed and will describe the analyses and procedures for accounting for missing, unused, and spurious data. This section is a summary of the planned statistical analyses of the primary, secondary and selected tertiary/exploratory endpoints.

### 9.4.1. Pharmacokinetic Analyses

#### 9.4.1.1. Derivation of Pharmacokinetic Parameters

The plasma PK parameters for PF-06882961 following single dose administration will be derived from the concentration-time profiles as detailed in [Table 3](#). Actual PK sampling times will be used in the derivation of PK parameters. In the case that actual PK sampling times are not available, nominal PK sampling time will be used in the derivation of PK parameters. The fraction of PF-06882961 unbound in plasma (fu) will be determined and reported for each participant by the analytical lab.

**Table 3. Plasma PK Parameters**

Parameter	Definition	Method of Determination
AUC last	Area under the plasma concentration-time profile from time zero to the time of the last quantifiable concentration (C last ).	Linear/Log trapezoidal method.
AUC inf*	Area under the plasma concentration-time profile from time zero extrapolated to infinite time.	AUC last + (C last * k el ), where C last* is the predicted plasma concentration at the last quantifiable time point estimated from the log-linear regression analysis.
C max	Maximum plasma concentration.	Observed directly from data.
T max	Time for C max .	Observed directly from data as time of first occurrence.
t 1/2 *	Terminal half-life.	Log e (2)/k el , where k el is the terminal phase rate constant calculated by a linear regression of the log-linear concentration-time curve. Only those data points judged to describe the terminal log-linear decline will be used in the regression.
CL/F*	Apparent clearance.	Dose/AUC inf .
V z /F*	Apparent volume of distribution.	Dose/(AUC inf *k el ).
fu	Fraction of unbound drug in plasma	C u /C (where C u represents unbound concentration and C represents total concentration).
AUC last,u	Unbound AUC 0-last	fu*AUC last .
AUC inf,u	Unbound AUC 0-inf	fu*AUC inf .
C max,u	Unbound C max	fu*C max .
CL u /F	Unbound CL/F	Dose/(AUC inf,u ).
V z,u /F	Unbound V z /F	Dose/(AUC inf,u *k el ).

\* as data permit

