#### **4.2. Scientific Rationale for Study Design**

This study involves participants with varying degrees of hepatic impairment and participants without hepatic impairment, matched for age as well as body weight (and gender as much as practically possible). A single dose of PF-06882961 is proposed, as single dose plasma PK of PF-06882961 is generally predictive of exposure upon repeated dosing and limited accumulation has been observed given the relatively short half-life of the compound.

Following administration of single doses of PF-06882961, the arithmetic mean terminal  $t_{1/2}$  of PF-06882961 ranged from 5-7 hours. Even with a possible modest increase in half-life, serial PK samples will be collected over 48 hours post-dose is expected to adequately characterize the elimination phase of the plasma concentration-time profile in the cohorts with varying degrees of hepatic function.

Based on a review of the effect of hepatic impairment on human pharmacokinetics for compounds cleared in a similar manner to PF-06882961 [CCI](#) mild hepatic impairment generally results in less than 2-fold increases in plasma exposure. In the same group of compounds, moderate hepatic impairment results in less than 3-fold increases in plasma exposure; however, overall, very limited clinical data are available regarding the effect of severe hepatic impairment [CCI](#) [15-17](#).

In this study, a single dose of PF-06882961 will be administered with a standard breakfast to reflect the conditions for anticipated use of PF-06882961 in the target T2DM population. Additionally, in study C3421001, variability based on geometric %CV for  $C_{max}$  was lower following administration with a high-fat meal (23% in the fed state, compared to 91% in the

fasted state). The adjusted geometric mean  $C_{max}$  was 57% lower (90% CI: 28%, 74%) in the fed state compared to the fasted state, while mean  $AUC_{inf}$  values were similar (approximately 12% lower in the fed state [90% CI: -5%, 26%]).

In general, participants with normal hepatic function (Cohort 1) will abstain from concomitant treatments, except for the treatment of adverse events. However use of selected limited prescription and non-prescription medications is permitted (refer to [Section 6.5](#) for details). COVID-19 specific assessments have been incorporated to minimize the risks of COVID-19 related complications to participants and the study site personnel.

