3. ENDPOINTS AND BASELINE VARIABLES: DEFINITIONS AND CONVENTIONS

Blood samples for PK analysis of PF-06882961 will be collected according to the Schedule of Activities given in the protocol.

PK parameters will be calculated (if possible) from the concentration-time data using standard non-compartmental methods.

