6.1. Primary Endpoint(s)

6.1.1. C_{max} , AUC_{inf} , AUC_{last} , fu for PF-06882961

6.1.1.1. Main Analysis

C_{max} , AUC_{inf} (if data permit), AUC_{last} and fu will be listed, summarized descriptively and analyzed by group for participants in the PK parameter set (as defined in Section 4). Missing values will be handled as detailed in Section 5.3.1.

A one-way analysis of variance (ANOVA) described in Section 5.2.3, that includes all 4 groups in the same model, will be used to compare the natural log transformed of C_{max} , AUC_{inf} , AUC_{last} and fu of PF-06882961 separately, for each of the hepatic impairment groups (Test, Groups 2, 3, 4) to the healthy normal hepatic function group (Reference, Group 1).

For summary statistics and median or mean plots by sampling time, the nominal PK sampling time will be used. For individual participant plots by time, the actual PK sampling time will be used. The plasma PK parameters of PF-06882961 for each group will be summarized as specified in Table 6 below.

Table 6. Summary statistics to be produced for Plasma PK Parameters of PF-06882961

Parameter	Summary Statistics
------------------	---------------------------

C_{max} , AUC_{inf} (if data permit), AUC_{last} and fu	N, arithmetic mean, median, $cv\%$, standard deviation, minimum, maximum, geometric mean and geometric $cv\%$.
--	--

Supporting data from the estimation of $t_{1/2}$ will be listed by group: terminal phase rate constant (k_{el}); goodness of fit statistic from the log-linear regression (r^2); the percent of AUC_{inf} based on extrapolation ($AUC_{extrap\%}$); and the first, last, and number of time points used in the estimation of k_{el} . This data may be included in the clinical study report.

The following plot will be presented:

- Box and whisker plots for individual PK parameters (AUC_{inf} , AUC_{last} , C_{max} and fu) will be constructed by group and overlaid with geometric means.

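### Does Table 3 of the protocol define AUCinf by multiplying the last concentration by kel, so that the extrapolated area is lost?

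*Protocol*

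**What the plan says.** Protocol section 9.4.1.1 refers to Table 3 for the derivation of the PK parameters. The AUCinf row reads "AUC last + (C last * k el", then a closing bracket and a where-clause. That clause defines Clast*, with an asterisk, which "is the predicted plasma concentration at the last quantifiable time point estimated from the log-linear regression analysis". In the half-life row, kel "is the terminal phase rate constant calculated by a linear regression of the log-linear concentration-time curve", and half-life is Loge(2)/kel, so kel is a rate per unit time.

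The SAP prints no formula for AUCinf. Its section 3 says the parameters are calculated from the concentration-time data "using standard non-compartmental methods". Section 6.1.1.1 lists kel, r², the time points used for kel and "the percent of AUC_{inf} based on extrapolation" as supporting data.

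For context, protocol section 4.2 reports that the mean terminal half-life after single doses "of PF-06882961 ranged from 5-7 hours", and that "serial PK samples will be collected over 48 hours post-dose". It allows for a modest lengthening of half-life. For similarly cleared compounds, it says that "moderate hepatic impairment results in less than 3-fold increases in plasma exposure".

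**The concern.** Taken at face value, the formula multiplies where it should divide. AUCinf is one of four primary endpoints and the parameter on which the precision table is based. It also feeds CL/F, Vz/F, AUCinf,u, CLu/F and Vz,u/F.

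With time in hours, the product is far smaller than the true tail, and the shortfall grows with half-life. If hepatic impairment slows elimination, the impaired cohorts would lose the most area and the Test/Reference ratio would be pulled towards 1. That is the wrong direction for a study meant to inform dosing recommendations in hepatic impairment. The extrapolation percentage, which is the check on tail quality, would read near zero for everyone.

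**Working it through.** **Does the point touch the sample size?** Protocol Table 2 gives 58% to 172% at a ratio of 100%. Inputs: SD 0.489, 6 per cohort, 4 cohorts (20 df), 90% CI, 80% coverage probability.

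Log half-width = t(0.95, 20) × 0.489 × √(χ²(0.80, 20)/20) × √(1/6 + 1/6) = 1.725 × 0.489 × 1.119 × 0.577 = 0.545. Then exp(±0.545) gives 58% and 172%. The other four rows reproduce as well. The calculation uses only the SD, so the AUCinf formula does not enter it.

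**Units.** Clast × kel is concentration/time. Clast/kel is concentration × time, the unit of an AUC. Only the quotient can be added to AUClast.

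**What the cell must mean.** The where-clause explains Clast*. That symbol occurs in the formula only if the asterisk after Clast belongs to it. On that reading the bracket holds Clast* and kel with no operator between them, and the missing operator is a slash. The table uses asterisks in three ways: as a product sign (AUCinf*kel), as the footnote mark for parameters derived as data permit, and as the label on Clast*. The Vz/F row, Dose/(AUCinf*kel), fits the standard AUCinf.

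**Size if someone coded the product, time in hours.** Literal tail / true tail = (Clast × kel)/(Clast/kel) = kel². Assume a mono-exponential profile quantifiable to 48 h, with true AUCinf set to 1. The tail share is exp(−48 kel), and the literal AUCinf is 1 − tail + kel² × tail.

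| Half-life | kel (per h) | kel² | Tail share | Literal/true AUCinf |
|---|---|---|---|---|
| 5 h | 0.1386 | 0.0192 | 0.13% | 0.999 |
| 7 h | 0.0990 | 0.0098 | 0.86% | 0.991 |
| 14 h (assumed) | 0.0495 | 0.0025 | 9.3% | 0.907 |
| 20 h (assumed) | 0.0347 | 0.0012 | 18.9% | 0.811 |

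Against a 7 h reference cohort, the ratio would be multiplied by 0.907/0.991 = 0.915 at 14 h and by 0.811/0.991 = 0.818 at 20 h.

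**A second model.** This used a one-compartment oral profile at the protocol's sampling times. Assumptions: absorption rate 0.7 per h, reference half-life 6 h, half-life prolonged through lower clearance, and the last three points used for kel.

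- Quantifiable to 48 h: literal AUCinf is 0.2% to 1.0% low at 5-7 h. The ratio is 1.88 instead of 2.01 at 12 h, and 2.52 instead of 3.02 at 18 h.
- Quantifiable only to 24 h: literal AUCinf is 4% to 11% low at 5-7 h. The ratios become 1.58 instead of 2.01 and 1.89 instead of 3.02.

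The documents give no lower limit of quantification, so both cut-offs are assumptions.

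**Time unit.** These factors hold only for time in hours. In days, a 5 h half-life gives kel = 0.693/(5/24) = 3.33 per day and kel² = 11, so the literal tail would be about 11 times too large. An expression whose error changes direction with the time unit cannot be what was intended.

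**The case for a change.** The best case for a correction is that Table 3 is the protocol's operative definition and neither document prints a correct one. The SAP writes out the unbound parameters that depend on AUCinf but leaves AUCinf itself to standard practice. Other slashes in the table are intact, as in Loge(2)/kel and Dose/AUCinf, and the asterisk does serve as a product sign elsewhere in it. Even with the asterisk read as a label, two adjacent symbols would normally be taken as a product. The repair is one character.

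Part of this stands. The cell as it reads is not a usable formula, and if half-life rose two- to three-fold the literal version would matter. But the surviving slashes prove little, because none of them follows a starred concentration, which is where a slash is easiest to lose in typesetting or in conversion of the PDF to text. The text alone cannot show which happened. The step from the misprint to biased results also fails. Someone would have to set aside the SAP's stated method, program a sum of incompatible units, and then overlook a listing in which the extrapolated percentage is near zero for every participant. At 14 h, for example, that listing would show 0.0025 × 9.3%/0.907, about 0.03%, instead of 9.3%.

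**Conclusion.** This is a clerical slip in the print, or a slash lost when the page was converted to text, and it calls for no change to the plan. The intended expression, AUClast + (Clast*/kel), can be recovered from the cell itself, from the units and from the SAP's choice of standard non-compartmental analysis. A look at the source page settles the notation.

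The expected effect on results is nil, on the assumption that the analyst follows the SAP. Were the product coded in hours, the loss would be about 1% or less of AUCinf at the documented 5-7 h half-life with concentrations quantifiable to 48 h. The larger figures, about 8% and 18% off a ratio, rest on half-lives of 14 h and 20 h that the documents do not report, and early loss of quantifiable samples would add to them. Cmax, AUClast, fu and the precision table do not depend on the formula.

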#### 9.4.1.2. Statistical Methods for Pharmacokinetic Data

The effect of varying degrees of hepatic impairment on PK parameters will be assessed by constructing 90% CIs around the estimated difference between each of the Test (hepatic impaired) cohorts and the Reference (without hepatic impairment) cohort. A 1-way analysis of variance (ANOVA) will be used to compare the natural log transformed PF-06882961 AUCinf, Cmax, AUClast, and fraction unbound (fu), as data permit, for each of the hepatic impairment cohorts (Test) to the cohort without hepatic impairment (Reference). Estimates of the adjusted mean differences (Test - Reference), and corresponding 90% confidence intervals, will be obtained from the model. These will be exponentiated to provide estimates of the ratio of adjusted geometric means (Test/Reference) and 90% confidence intervals for the ratios.

Additional exploratory analysis using linear regression will be used to analyze the potential relationship between appropriate PK parameters [eg,  $AUC_{inf}$ ,  $AUC_{last}$ ,  $C_{max}$  and  $fu$ ] and hepatic function (eg, serum albumin concentration, prothrombin time or total bilirubin). Plots of PK parameters (eg,  $AUC_{inf}$ ,  $AUC_{last}$ ,  $C_{max}$  and  $fu$ ) versus hepatic function will be constructed, with a regression line and 90% confidence region included. Estimates of the slope and intercept, together with a 90% CI, and the coefficient of determination (ie,  $R^2$  and adj- $R^2$ ) will be obtained from the model.

Additionally, as an exploratory analysis, age and body weight may be explored as an additional covariate/factor in the models, as appropriate.

Individual PF-06882961 concentrations will be listed and summarized descriptively by nominal PK sampling time and hepatic function cohort. Individual participant and summary profiles of the concentration-time data will be plotted by hepatic function cohort for both total plasma PF-06882961 and unbound PF-06882961.

PF-06882961  $AUC_{inf}$ ,  $AUC_{last}$ ,  $C_{max}$ , unbound  $AUC_{inf}$  ( $AUC_{inf,u}$ ), unbound  $AUC_{last}$  ( $AUC_{last,u}$ ), and unbound  $C_{max}$  ( $C_{max,u}$ ) individual participant parameters will be plotted by hepatic function cohort. PK parameters of PF-06882961 will be summarized descriptively by hepatic function cohort. Unbound fraction ( $fu$ ) will be listed and summarized descriptively by hepatic function cohort.

#### **9.4.2. Safety Analyses**

All safety analyses will be performed on the safety population.

AEs, ECGs, BP, pulse rate, and safety laboratory data will be reviewed and summarized on an ongoing basis during the study to evaluate the safety of participants. Any clinical laboratory, ECG, BP, and pulse rate abnormalities of potential clinical concern will be described. Safety data will be presented in tabular and/or graphical format and summarized descriptively, where appropriate.

Medical history and physical examination and neurological examination information, as applicable, collected during the course of the study will be considered source data and will not be required to be reported, unless otherwise noted. However, any untoward findings identified on physical and/or neurological examinations conducted during the active collection period will be captured as AEs, if those findings meet the definition of an AE.

Data collected at screening that are used for inclusion/exclusion criteria, such as laboratory data, ECGs, and vital signs, will be considered source data, and will not be required to be reported, unless otherwise noted. Demographic data collected at screening will be reported. COVID-19 specific assessments data will be considered source data and will not be required to be reported.

#### **9.4.2.1. Electrocardiogram Analyses**

Changes from baseline for the ECG parameters QT interval, heart rate, QTcF interval, PR interval, and QRS complex will be summarized by hepatic function cohort.

The number (%) of participants with maximum postdose QTcF values and maximum increases from baseline in the following categories will be tabulated by hepatic function cohort:

#### **Safety QTcF Assessment**

Degree of Prolongation	Mild (msec)	Moderate (msec)	Severe (msec)
Absolute value	>450-480	>480-500	>500
Increase from baseline		30-60	>60

#### **9.4.3. Other Analyse(s)**

Pharmacogenomic or biomarker data from Banked Biospecimens may be collected during or after the trial and retained for future analyses; the results of such analyses are not planned to be included in the CSR.

### **9.5. Interim Analyses**

No formal interim analysis will be conducted for this study. As this is an open-label study, the sponsor may conduct unblinded reviews of the data during the course of the study for the purpose of safety assessment, facilitating PK modeling, and/or supporting clinical development.

### **9.6. Data Monitoring Committee or Other Independent Oversight Committee**

This study will not use a data monitoring committee (DMC).

## **10. SUPPORTING DOCUMENTATION AND OPERATIONAL CONSIDERATIONS**

### **10.1. Appendix 1: Regulatory, Ethical, and Study Oversight Considerations**

#### **10.1.1. Regulatory and Ethical Considerations**

This study will be conducted in accordance with the protocol and with the following:

- Consensus ethical principles derived from international guidelines including the Declaration of Helsinki and CIOMS International Ethical Guidelines;
- Applicable ICH GCP guidelines;
- Applicable laws and regulations, including applicable privacy laws.

The protocol, protocol amendments, ICD, SRSD(s), and other relevant documents (eg, advertisements) must be reviewed and approved by the sponsor and submitted to an IRB/EC by the investigator and reviewed and approved by the IRB/EC before the study is initiated.

Any amendments to the protocol will require IRB/EC approval before implementation of changes made to the study design, except for changes necessary to eliminate an immediate hazard to study participants.

The investigator will be responsible for the following:

- Providing written summaries of the status of the study to the IRB/EC annually or more frequently in accordance with the requirements, policies, and procedures established by the IRB/EC;
- Notifying the IRB/EC of SAEs or other significant safety findings as required by IRB/EC procedures;
- Providing oversight of the conduct of the study at the site and adherence to requirements of 21 CFR, ICH guidelines, the IRB/EC, European regulation 536/2014 for clinical studies (if applicable), and all other applicable local regulations.

#### **10.1.1.1. Reporting of Safety Issues and Serious Breaches of the Protocol or ICH GCP**

In the event of any prohibition or restriction imposed (ie, clinical hold) by an applicable regulatory authority in any area of the world, or if the investigator is aware of any new information that might influence the evaluation of the benefits and risks of the study intervention, Pfizer should be informed immediately.

In addition, the investigator will inform Pfizer immediately of any urgent safety measures taken by the investigator to protect the study participants against any immediate hazard, and of any serious breaches of this protocol or of ICH GCP that the investigator becomes aware of.

### **10.1.2. Financial Disclosure**

Investigators and subinvestigators will provide the sponsor with sufficient, accurate financial information as requested to allow the sponsor to submit complete and accurate financial certification or disclosure statements to the appropriate regulatory authorities. Investigators are responsible for providing information on financial interests during the course of the study and for 1 year after completion of the study.

### **10.1.3. Informed Consent Process**

The investigator or his/her representative will explain the nature of the study to the participant and answer all questions regarding the study. The participant should be given sufficient time and opportunity to ask questions and to decide whether or not to participate in the trial.

Participants must be informed that their participation is voluntary. Participants will be required to sign a statement of informed consent that meets the requirements of 21 CFR 50, local regulations, ICH guidelines, HIPAA requirements, where applicable, and the IRB/EC or study center.

The investigator must ensure that each study participant is fully informed about the nature and objectives of the study, the sharing of data related to the study, and possible risks associated with participation, including the risks associated with the processing of the participant's personal data.

The participant must be informed that his/her personal study-related data will be used by the sponsor in accordance with local data protection law. The level of disclosure must also be explained to the participant.

The participant must be informed that his/her medical records may be examined by Clinical Quality Assurance auditors or other authorized personnel appointed by the sponsor, by appropriate IRB/EC members, and by inspectors from regulatory authorities.

The investigator further must ensure that each study participant is fully informed about his or her right to access and correct his or her personal data and to withdraw consent for the processing of his or her personal data.

The medical record must include a statement that written informed consent was obtained before the participant was enrolled in the study and the date the written consent was obtained. The authorized person obtaining the informed consent must also sign the ICD.

Participants must be reconsented to the most current version of the ICD(s) during their participation in the study.

A copy of the ICD(s) must be provided to the participant.

Participants who are rescreened are required to sign a new ICD.

Unless prohibited by local requirements or IRB/EC decision, the ICD will contain a separate section that addresses the use of samples for optional additional research. The optional additional research does not require the collection of any further samples. The investigator or authorized designee will explain to each participant the objectives of the additional research. Participants will be told that they are free to refuse to participate and may withdraw their consent at any time and for any reason during the storage period. A separate signature will be required to document a participant's agreement to allow specimens to be used for additional research. Participants who decline to participate in this optional additional research will not provide this separate signature.

